5.2. Primary Efficacy Endpoint

5.2.1. Definition

The primary effectiveness endpoint is the change in the KCCQ-TSS from baseline to Week 12.

5.2.2. Estimand

The primary estimand, the main clinical quantity of interest to be estimated in the study, is defined by the following 5 attributes (ICH E9 [R1]).⁴

- Population: FAS: all randomized participants with HF (who either have HF_rEF or HF_pEF, regardless of T2DM status) with at least one dose of study intervention and at least 1 post-baseline KCCQ measurement
- Treatment: canagliflozin 100 mg or placebo
- Variable: change from baseline to Week 12 post first dose in the KCCQ-TSS
- Intercurrent events: treatment discontinuations (either due to AE or other reasons) or treatment switching; use treatment policy strategy to address intercurrent events (i.e., use all available measurements collected during Week 12, regardless of the occurrence of the intercurrent event); events of “loss to follow up” or “study withdrawal” or “death” are not considered intercurrent events but rather missing data.
- Population-level summary: difference in mean change from baseline to Week 12 in the KCCQ-TSS between randomized groups.

In other words, the main quantity to estimate for the primary effectiveness endpoint is the mean difference between the 2 treatment groups (canagliflozin 100 mg and placebo) of the change from baseline to Week 12 in the KCCQ-TSS.

5.2.3. Analysis Methods

The primary effectiveness endpoint analysis will be based on the full analysis set (FAS).

Considering the repeated measurements of the KCCQ-TSS in the double-blind treatment period (ie, at baseline, Weeks 2, 4, 6, and 12 respectively), the primary effectiveness endpoint (change in the KCCQ-TSS from baseline to Week 12) will be analyzed by a MMRM method simultaneously adjusting for treatment, stratification factor (HF_rEF or HF_pEF), time, time by treatment, and baseline KCCQ-TSS value as covariates. Time is repeated within participants and an unstructured covariance structure will be assumed across treatment groups to model the within-participant errors. Fixed effects tests will be computed using the Kenward-Roger method to determine the degrees of freedom of the denominator. In case of convergence issues, alternative variance-covariance structures will be evaluated in the following order, with the first structure in the following list that converges being used in the analysis: heterogeneous Toeplitz, standard Toeplitz, and AR (1) with separate participant random effect. The primary comparison will be based on the difference in the LS mean changes from baseline to Week 12 between treatments. The treatment difference in the LS means, corresponding 95% confidence intervals (CI) and associated p-value will be calculated. The LS means \pm SE of change from baseline values estimated by MMRM will be plotted by each timepoint for each intervention group.

```
PROC MIXED DATA=analysis_dataset;
CLASS treatment time ptid;
MODEL change = treatment time treatment*time baseline strat_var/DDFM=KR;
REPEATED time / SUBJECT=ptid TYPE=UN;
LSMEANS treatment;
LSMEANS treatment*time/pdiff cl;
RUN;
```

An MMRM model assumes the KCCQ-TSS data missing at random (MAR). A sensitivity analysis may be performed involving multiple imputation (MI) modeling approach for missing KCCQ-TSS values when the MAR assumption is considered not valid. Implementing the MI process requires 3 steps: 1) each missing value is imputed multiple times, based on statistical modeling, resulting in repetitions of the original dataset, along with the newly imputed values (implemented in the Statistical Analysis System [SAS] using PROC MI); 2) each dataset is analyzed using an MMRM model (implemented in SAS using PROC MIXED). The LS means and SEs from each analysis will be output to a SAS dataset; 3) results from the analyses performed on multiple datasets in step #2 are combined to provide valid statistical inference (implemented in SAS using PROC MIANALYZE).¹

A complete SAS code for MMRM model and implementation of the MI approach described above will be added to the final SAP appendix or to the final study report. Mortality in this short-duration trial is expected to be low and to be comparable between groups and will be ignored in the primary analyses of mean differences in changes in KCCQ total symptom scores, but can be included in the responder analyses (described below) by assigning them to the lowest response (greatest deterioration) category. Should there be a >5% mortality rate in this study, and if it is unequally distributed between treatment arms, then joint modeling of survival and health status (e, g., KCCQ) will be performed. A win-ratio approach^{19,20} may also be considered by analyzing the KCCQ-TSS score as a composite, rank-based outcome, incorporating participant vital status at 12 weeks along with a change in score from baseline to 12 weeks in surviving participants. This essentially is the rank analysis of covariance method, with a corresponding win ratio used to estimate the magnitude of treatment effect.

An exploratory responder analysis will be performed when comparing proportions of participants with a 5- (or 10-) point improvement in the KCCQ-TSS from baseline to Week 12 between the groups. This will be based on a 2-sample difference in proportions test along with a 95% confidence interval for the difference in 2 proportions.

The mean differences between the groups will be augmented with both responder analyses and empirical cumulative distribution and probability density function curves. Specifically, the empirical cumulative distribution function (CDF) of the change from baseline in KCCQ-TSS will be generated. CDF shows the proportion of the population scoring less than or equal to each possible change score. CDFs are useful as they graphically characterize the treatment effect or differences between groups. It also enables a ready assessment of different magnitudes of clinical change (e.g., 5, 10, and ≥ 20 -point changes, corresponding with small to moderate, moderate to large, and large to very large clinical changes). CDFs and histograms will be shown for changes from baseline to Week 12 in the KCCQ TSS. For all CDF plots, the x-axis is the score change from baseline to final time point (i.e., Week 12) for the KCCQ-TSS. The y-axis is the cumulative proportion of the participants in each of the corresponding categories that reach the score change on the x-axis.

According to the Food and Drug Administration's (FDA's) guidance on PRO measures, a responder is defined by the empirically determined score change in a measure, experienced by an individual patient over a predetermined time period that has been demonstrated in the target

population to have a significant treatment benefit. This is also often referred to as responsiveness or ability of the PRO measure to capture the true underlying change in the patient health status over time. Assessing the responsiveness of the PRO measure using an anchor-based approach involves comparing the changes in the PRO scores to other clinically meaningful markers or anchors that represent a valid measure of clinical change.

For the anchor-based analysis of the KCCQ-TSS endpoint, participants will be characterized based on the PGIC scores at Week 12. The mean change in KCCQ-TSS endpoint observed in the smallest improvement category of the PGIC will be examined as a key anchor-based indicator of a responder. The definition for a small improvement in PGIC is given as those who improve by one category (i.e., from “a little improved” to “somewhat improved”). Specifically, the retrospective PGIC responses of “3=a little improved” will be selected to represent time points where participants register meaningful changes in their HF symptoms. Each time a participant responds with a PGIC score of “3=a little improved”, a KCCQ-TSS change score from the preceding visit is computed. For the double-blind treatment period, the PGIC will be collected at 4 time points (i.e., Weeks 2, 4, 6, and 12 respectively) which can yield between zero and 4 KCCQ-TSS change scores by each participant. For each participant with at least one PGIC response of “3=a little improved”, a mean of the individual participant’s KCCQ-TSS change scores is computed. A summary of KCCQ-TSS change scores across PGIC categories¹⁶ will then be presented.

The KCCQ-TSS change scores may also be standardized into effect size (ES) statistics by dividing them by their SD at baseline. The following cutoff values will be used to interpret effect size: small ES = 0.2, moderate ES = 0.5, and large ES = 0.8. Together with the CDF, results from the anchor-based methods will be examined and a single responder definition threshold will be determined, if the results from the anchor-based assessments in this study differ substantially from prior studies examining the clinical meaningfulness of changes in the KCCQ.

In addition, a distribution-based change (i.e., minimum detectable [MID] change) may be explored for which the KCCQ-TSS can be derived using the baseline SD. Generally, a value of half the baseline SD has been frequently found to correspond to the MID obtained via the anchor-based method. A value of $0.2 \times \text{SD}$ may also be examined.

Subgroup analyses for the change from baseline to Week 12 for the primary effectiveness endpoint will be conducted for subgroups (listed in Section 2.4) based on all randomized analysis set. These analyses will assess consistency of the overall treatment effect across subgroup variables.

The main MMRM analyses will be repeated with each subgroup tested separately. Intervention group differences of LS means as well as corresponding 95% CIs within each subgroup level will be presented.

The intervention-by-subgroup interaction p-value will be estimated using a separate MMRM model including intervention, baseline KCCQ value, stratification factor (HFrEF/HFpEF), subgroup, and intervention-by-subgroup interaction term(s). Interactions with p-value < 0.1 will be investigated further to determine the nature of interaction (quantitative or qualitative) and the

association with other subgroups. For qualitative interactions, Gail and Simon (1985) approach¹⁵ may be considered.

Results will be presented in a summary table and in a forest plot. The forest plot will display the “overall” treatment effect, based on the main MMRM analysis, as a reference line. LS means of the intervention group differences, the corresponding 95% CIs, and the numbers of participants in the subgroup levels will be presented in the forest plot.

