9.2. Sample Size Determination

The primary effectiveness endpoint is the change from baseline in the KCCQ TSS at the end of the 3-month double-blind treatment period. Although a 5-point improvement in the KCCQ TSS is generally viewed as clinically meaningful,^{5,29} recent studies^{16,21} have shown that improvements in the range of 3 to 5 points on the KCCQ TSS are equally meaningful in the overall HF-related health status measured by the KCCQ over a 12-week time period. Based on the evidence from these studies, the current study is powered to detect a mean change from baseline of 3 points in the KCCQ TSS between canagliflozin 100 mg and placebo groups at 12 weeks. Assuming a significance level of 5% and a standard deviation of 18 points for mean change in KCCQ TSS, a total of 1,900 participants will be randomized in this study providing approximately 95% power. This sample size is adequate to account for a potential 5% dropout rate.

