1.2. Study Design

OVERALL DESIGN

This is a randomized, double-blind, placebo-controlled, decentralized, virtual, superiority study conducted in the US in participants with symptomatic HF (stratified by heart failure with HFrEF or HFpEF). This study examines the improvement in the KCCQ-TSS after 12 weeks of treatment with canagliflozin 100 mg or placebo. The study will continue for an additional 6 months without further study intervention to collect participant follow-up data from the smartphone, Fitbit, and claims in a real-world setting. At the end of the 12-week, double-blind treatment period, participants will be informed about their actual treatment allocation, whether they had been randomized to canagliflozin or placebo.

The study will enroll participants from large integrated health networks (IHNs) and physician practices in the US with the participants conducting many of their study-related activities through an app on a smartphone and will provide daily activity data recorded by using a Fitbit device. There will be no in-person clinic visits required by the study (see [Appendix 3: Schedule of Activities](#)).

[figure not shown]
The study consists of a screening period, a 12-week double-blind treatment period, and a 6-month follow-up (no intervention) observational period for each participant. Approximately 1,900 participants are planned for randomization into the study in a 1:1 ratio to canagliflozin 100 mg daily or placebo groups (950 in each study intervention group). After Week 12 (i.e., the end of the double-blind treatment period), the study will continue for an additional 6 months when study intervention will no longer be provided. Randomization will be performed using the interactive web response system (IxR). Participants will be stratified based on HF ejection fraction (EF) type – HFrEF or HFpEF.

Data collection from the smartphone, Fitbit device, and claims will continue until Month 9 for all endpoints. Specifically, study assessments include the following: KCCQ, PGIC, PGI-S, and an

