1.4. Sample Size Justification

The primary effectiveness endpoint is the change from baseline in the KCCQ-TSS at the end of the 12-week double-blind treatment period. Although a 5-point improvement in the KCCQ-TSS is generally viewed as clinically meaningful,^{2,12} recent studies^{7,8} have shown that improvements in the range of 3 to 5 points on the KCCQ-TSS are equally meaningful in the overall HF-related health status measured by the KCCQ over a 12-week time period. In considering the clinical significance of scores, it is important to separate mean changes for groups of participants, as compared with intra-individual changes. On the TSS, there are 7 items (4 for symptom frequency and 3 for severity/burden).^{3,11} Shifting a response on KCCQ questions 5 and 7 shifts the TSS score by 2.083 points on a 100-point scale. A shift in response for questions 3 and 9 shifts the score by 3.125 points and for items 4, 6, and 8, shifts the score by 4.166 points, assuming no missing responses. Thus, an intra-individual change of at least 2 categories (3 if the only change is in items 5 and 7) would exceed the 5-point threshold that has been shown to be clinically significant. When analyzing groups of participants, the mean difference across the entire population includes a distribution of participants with different magnitudes of individual change and a 3- to 5-point difference between groups reflects a significantly larger proportion of participants in one group, as compared with the other, who have clinically important improvements in their TSS.

Thus, based on the totality of evidence evaluating the clinical significance of the KCCQ,^{5,6,9,14} a between group difference of 3 points is considered clinically meaningful and the current study is powered to detect a mean change from baseline of 3 points in the KCCQ-TSS between canagliflozin 100 mg and placebo groups at Week 12. Assuming a significance level of 5% and a

standard deviation (SD) of 18 points for mean change in KCCQ-TSS, a total of 1,900 participants will be randomized in this study providing approximately 95% power. This sample size is adequate to account for a potential 5% to 10% dropout rate - that is, with a dropout as high as 10% [$n=1,710$], the statistical power remains $>90\%$.

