5.1.1. Level of Significance

A 5% level of significance will be used for all analyses. All statistical tests and 95% confidence intervals presented in the analyses of endpoints will be 2-sided.

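### The primary MMRM is valid but uses one baseline slope for all four visits; a baseline-by-time term could give a small precision gain at Week 12 for almost no cost

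*SAP*

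**What the plan says.** SAP 5.2.3 (Analysis Methods) lists the primary model's terms as treatment, stratification factor, time, "time by treatment, and baseline KCCQ-TSS value as covariates". Its PROC MIXED code agrees: "MODEL change = treatment time treatment*time baseline strat_var/DDFM=KR". Protocol 9.4.2.1 and the protocol synopsis list the same covariates, and none of these places has a baseline-by-time term. The covariance is unstructured over Weeks 2, 4, 6 and 12, and the treatment effect may differ at each visit. The primary comparison is the LS-mean difference at Week 12 alone.

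SAP 5.3.3 uses a model of the same kind for the KCCQ domain and summary scores. It also uses one for daily step count, with baseline average step count as the covariate.

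The sample size takes no credit for baseline adjustment. Protocol 9.2 is based on the raw change score: "Assuming a significance level of 5% and a standard deviation of 18 points for mean change in KCCQ TSS".

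**The concern.** The model lets everything vary by visit except the baseline slope. With an unstructured covariance, that slope is a generalised-least-squares average over the four visits. If a score's link with its baseline weakens over follow-up, the average sits near the Week 2 to Week 6 slopes and away from the Week 12 slope. The Week 12 contrast is then adjusted with a coefficient that does not suit it. Its residual variance is somewhat larger than it need be, and part of any chance baseline imbalance stays in the estimate.

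What is at stake is efficiency. SAP 1.4 expects about 400-480 participants instead of 1,900, so a cheap gain is worth considering, although it would be far too small to offset that shortfall.

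**Working it through.** **1. The plan's own power figures.** Inputs: 1:1 allocation (SAP 1.2), SD 18 (protocol 9.2, SAP 1.4), two-sided 5% (SAP 5.1.1). Formula: SE = 18 × √(4/N); power ≈ Φ(difference/SE − 1.96).

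| N | Difference | SE | Power | Stated |
|---|---|---|---|---|
| 1,900 | 3 | 0.826 | 95.3% | about 95% |
| 1,710 | 3 | 0.871 | 93.1% | above 90% |
| 400 | 3.5 | 1.800 | 49.4% | 50% |
| 445 | 4.8 | 1.707 | 80.3% | at least 80% |

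All reproduce.

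**2. Variance penalty of a common slope.** Let b be the vector of true visit-specific baseline slopes and S the residual covariance of the visits given baseline. With complete data:

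- common slope: b_c = (1′S⁻¹b)/(1′S⁻¹1)
- Week 12 residual variance, common slope: S₁₂ + Var(baseline) × (b₁₂ − b_c)²
- Week 12 residual variance, slope by visit: S₁₂

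Analysing change instead of the raw score lowers every slope by 1, so b₁₂ − b_c is unaffected. With equal SDs at all visits, slopes equal correlations and the variance ratio is 1 + (b_c − b₁₂)²/(1 − b₁₂²).

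The documents give none of these correlations, so the following are assumptions: inter-visit correlation 0.85 minus 0.02 per week apart, and baseline correlation falling linearly from Week 2 to Week 12, either by visit number or by week.

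| Baseline correlation, Week 2 to Week 12 | b_c (by week) | Ratio, by visit number | Ratio, by week |
|---|---|---|---|
| 0.85 to 0.60 | 0.81 | 1.060 | 1.067 |
| 0.80 to 0.60 | 0.75 | 1.031 | 1.035 |
| 0.80 to 0.65 | 0.75 | 1.016 | 1.019 |
| 0.80 to 0.70 | 0.76 | 1.007 | 1.008 |
| 0.75 to 0.65 | 0.71 | 1.006 | 1.007 |
| 0.75 to 0.70 | 0.73 | 1.001 | 1.002 |
| 0.70 throughout | 0.70 | 1.000 | 1.000 |

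Example, first row by week: (0.807 − 0.60)²/(1 − 0.36) = 0.043/0.64 = 0.067. In participants this is 0.067 × 400 ≈ 27 to 0.067 × 480 ≈ 32 at the top of the table, and none at the bottom.

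**3. Sensitivity to visit SDs.** A slope is a correlation times an SD ratio, so a growing visit SD offsets a falling correlation. If the SD rises linearly to 1.1 or 1.2 times its baseline value by Week 12, the 0.80-to-0.65 ratio falls from 1.019 to 1.008 and 1.002. The 0.75-to-0.65 ratio falls from 1.007 to 1.002 and 1.000. Shrinking SDs enlarge the gain.

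**4. Effect on power.** A separate set of assumed patterns, scaled so that the SD of change at Week 12 is 18, evaluated at N=445 and a 4.8-point difference:

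| Pattern (baseline correlation) | Excess SE, common slope | Power, common slope → by visit |
|---|---|---|
| Equal slopes (0.70) | 0.0% | 86.2% → 86.2% |
| Mild decay (0.78 to 0.62) | 1.0% | 87.3% → 87.9% |
| Mild, visit SD grows 20% | 0.1% | 83.0% → 83.1% |
| Mild, visit SD shrinks 20% | 2.7% | 94.0% → 95.1% |
| Moderate (0.77 to 0.51) | 2.2% | 88.7% → 90.0% |
| Steep (0.77 to 0.43) | 3.2% | 89.6% → 91.3% |
| Extreme: very steep (0.74 to 0.28) | 5.1% | 91.6% → 94.0% |
| Extreme: near-AR(1), no measurement noise (0.89 to 0.49) | 7.5% | 85.7% → 90.2% |

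Both models exceed the unadjusted 80.3% because both adjust for baseline. At N=1,900 and 3 points the gain is at most 1.4 power points.

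**5. Validity.** Simulated trials: N=445, 2,000 runs per setting, dropout 0-20%, missing at random and alike in both arms. Rejection under the null was 4.5-6.0% for both models (simulation SE √(0.05 × 0.95/2,000) ≈ 0.5 points), and bias was at most 0.07 points. SE ratios, common slope to by-visit, were 0.999 (equal slopes), 1.009-1.012 (mild) and 1.031-1.038 (steep). One setting (steep decay, 4.8 points, 20% dropout) did not finish.

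**6. Chance imbalance.** With equal SDs and SD of change 18, the baseline SD is 18/√(2(1 − b₁₂)): 20.1 for 0.60 and 23.2 for 0.70. One SE of baseline imbalance at N=445 is that SD × √(4/445), or 1.9 to 2.2 points. Multiplied by b_c − b₁₂, the shift in the Week 12 estimate is about 0.13 to 0.40 points in the first five rows of the step 2 table. It averages to zero over randomisations.

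**The case against.** The strongest reply is that nothing is wrong. Protocol and SAP agree on the covariates, treatment is randomised, and the treatment-by-time effects are saturated. An averaged slope therefore affects a nuisance coefficient and does not invalidate the test. That stands. A reader might infer that the Week 12 treatment estimate is biased or incorrectly modelled, but the simulations show no difference in bias or type I error. They did not cover dropout that differs by arm.

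The second reply is that a weakening baseline link is general expectation and is not shown in these documents. That also stands. A reader might infer that the extra term is certain to recover precision, but the gain is nil with equal slopes and close to nil if visit SDs grow modestly.

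Third, the change is not literally free: it uses three parameters, and the SE is about 0.1% larger if slopes are equal.

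Fourth, no figure in SAP 1.4 depends on baseline adjustment, and a gain of this size does not repair the enrolment shortfall. Both statements are correct. What remains is a small possible gain set against a smaller cost.

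**Conclusion.** The point holds as a minor efficiency refinement and is not an error in the plan. In ordinary patterns, the single slope costs between 0% and about 6-7% of the Week 12 variance. That is 0 to about 3% of the SE, or roughly 0 to 2 power points at N=445 and 4.8 points. Losses of 5-7% of the SE need extreme patterns. The lower end is exactly zero when slopes are equal.

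The range rests on assumed baseline-by-visit correlations, inter-visit correlations, visit SDs and normal data. The documents supply none of these, so the gain in this trial cannot be estimated from them. No corresponding calculation was made for step count. The stated power figures stand.

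**What to change.** Add `baseline*time` to the MODEL statement in SAP 5.2.3 and to the text above it, and carry it into the KCCQ domain and summary-score MMRMs in SAP 5.3.3. With four post-baseline visits this is three extra parameters. Optionally add baseline step count by time to the step-count MMRM. SAP Table 1 gives five post-baseline two-week intervals to Week 12, so that is four extra parameters. Align the covariate list in protocol 9.4.2.1 and the synopsis.

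Fix the change before anyone involved in the analysis sees data by treatment arm. SAP section 3 reports the 12-week data first, so the deadline is that analysis and not the 9-month report.

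The cost for KCCQ is a few degrees of freedom (the critical t moves from 1.96537 at 440 df to 1.96541 at 437 df) and an SE about 0.1% larger if slopes prove equal. The sample-size section needs no change.

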5.3.3. Analysis Methods

Daily step counts and daily floors climbed data at baseline will be presented as 14-day averages of daily counts starting with the first dose date and ending with Day 14 during the double-blind treatment period. This method of averaging will continue until end of Month 9 (Day 252) or, until the time of end of study (EOS) observation is available.

The above two key secondary endpoints will be analyzed in two ways –

- 1) following the same approach as employed for the primary effectiveness endpoint (i.e. using an MMRM model adjusting for baseline covariates such as treatment, stratification factor and baseline average step count).
- 2) by calculating mean change from baseline to Week 12 in daily step counts using the corresponding 14-day averages at baseline and Week 12 respectively. That is, the mean difference in the 14-day averages in daily step counts or daily floors climbed is calculated for each randomized intervention group and difference in mean changes between the 2 randomized intervention groups will be compared using a 2-sided t-test.

As stated in Section 1.3, the first key secondary endpoint of daily step count will be tested once the primary endpoint is shown to be statistically significant at 5% significance level.

Other secondary endpoints refer to changes in the KCCQ individual domain scores (physical limitation, quality of life), and the KCCQ clinical summary and overall summary scores from baseline to Week 12. The individual KCCQ domain scores as well as the summary scores will be produced at each time point (based on the KCCQ algorithm) with changes from baseline calculated at each specified post-baseline time point. For these endpoints, an MMRM model (like that specified for the analysis of the primary endpoint) will be employed to summarize changes over time from baseline to Week 12. Hypotheses related to these domains will be independently tested at 5% without any control for overall type I error rate.

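### If both the unstructured and the heterogeneous Toeplitz fits fail, the SAP's remaining fallbacks force one variance on all visits with no robust SE, so the Week 12 error rate depends on an unstated SD pattern

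*SAP*

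**What the plan says.** SAP 5.2.3 fits change in KCCQ-TSS at Weeks 2, 4, 6 and 12 with an unstructured within-participant covariance. "Fixed effects tests will be computed using the Kenward-Roger method to determine the degrees of freedom of the denominator". If there are convergence problems, the analysis takes the first structure that converges from an ordered list: "heterogeneous Toeplitz, standard Toeplitz, and AR (1) with separate participant random effect". Neither the text nor the PROC MIXED code asks for an empirical (sandwich) standard error. Protocol 9.4.2.1 names unstructured covariance only, so the fallback rule exists only in the SAP.

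The same model is used elsewhere. For subgroups, "The main MMRM analyses will be repeated with each subgroup tested separately" (SAP 5.2.3). Step count is analysed "following the same approach as employed for the primary effectiveness endpoint" (SAP 5.3.3), and the KCCQ domain scores by a similar MMRM. On the error rate, SAP 5.1.1 states: "A 5% level of significance will be used for all analyses" and "All statistical tests and 95% confidence intervals presented in the analyses of endpoints will be 2-sided".

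**The concern.** The tested contrast is at the last visit. Standard Toeplitz, and AR(1) with a participant effect, describe all four visits with a single variance. The Week 12 standard error then comes from a variance pooled over visits, not from the Week 12 variance. If change scores spread out with time, that standard error is too small and the test rejects too often. Kenward-Roger corrects for small samples. It does not protect against a wrong covariance structure.

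A rising spread is plausible here. The response is change from baseline with baseline as a covariate, so its residual variance grows as the correlation with baseline fades. The documents give no figure for this. What is at stake is whether a p-value and confidence interval from the second or third fallback hold the stated 5% and 95%.

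**Working it through.** **Inputs from the documents**
- Two-sided 5% level (SAP 5.1.1).
- "standard deviation (SD) of 18 points for mean change in KCCQ-TSS", and "a between group difference of 3 points is considered clinically meaningful" (SAP 1.4).
- 1,900 participants planned, 1:1; 400 to 480 now anticipated; dropout 5% to 10% (SAP 1.2 and 1.4).
- Post-baseline visits at Weeks 2, 4, 6 and 12 (SAP 5.2.3), so the gaps are 2, 2 and 6 weeks.

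**Assumed:** the SDs at Weeks 2, 4 and 6, and the correlations between visits.

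**1. The plan's own figures.** With 950 per arm, SE = 18 × √(2/950) = 0.826, and power = Φ(3/0.826 − 1.96) = Φ(1.67) = 95.3%, against the stated 95% or so. With N = 445 and a difference of 4.8, SE = 18 × √(4/445) = 1.707 and power = Φ(0.853) = 80.3%, against the stated 80%. So 18 is used as the Week 12 SD, and it is the only SD given.

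**2. Direct approximation.** With one common variance, the fitted SD is close to the root mean square of the visit SDs. Then

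actual error = 2 × Φ(−1.96 × pooled SD / 18).

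For 12/14/15/18: pooled variance = (144 + 196 + 225 + 324)/4 = 222.25, pooled SD = 14.91, ratio = 0.828, error = 2 × Φ(−1.623) = 10.5%.

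**3. Fitted structures, large sample.** For each SD pattern, the closest standard Toeplitz and AR(1)-plus-participant covariances under the Gaussian likelihood were found, and their Week 12 standard error was compared with the true one. The two structures agree closely. The last column spans several correlation patterns, with 0% and 10% dropout.

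| Assumed SDs, Weeks 2/4/6/12 | Pooled SD | Ratio to 18 | Error, step 2 | Error, step 3 |
|---|---|---|---|---|
| 20/19.5/19/18 | 19.14 | 1.063 | 3.7% | 3.7–3.8% |
| 18/18/18/18 | 18.00 | 1.000 | 5.0% | 5.0–5.1% |
| 16/17/17.5/18 | 17.14 | 0.952 | 6.2% | 6.2–6.5% |
| 15/16/17/18 | 16.54 | 0.919 | 7.2% | 7.2–7.4% |
| 12/14/15/18 | 14.91 | 0.828 | 10.5% | 10.1–10.7% |
| 10/12/14/18 | 13.82 | 0.768 | 13.2% | 12.4–13.6% |

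**4. Heterogeneous Toeplitz, the first fallback.** It has a separate variance per visit, so unequal SDs do not matter. It does assume equal spacing. With correlation c + (1 − c) × 0.7^(gap/2 weeks) and c from 0.3 to 0.5, its Week 12 standard error is 7% to 9% too large. The error is 2 × Φ(−1.96 × 1.09) = 3.3% at c = 0.3, and 3.5% at c = 0.5. Another pattern that follows the actual week gaps gave 2.9%. It errs on the safe side.

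**5. Simulation.** N = 440, no treatment effect, 10% dropout, 2,500 trials per setting (Monte Carlo SE about 0.4 points), rejection at Week 12:

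| Assumed SDs | Unstructured | Heterogeneous Toeplitz | Standard Toeplitz or AR(1) + participant | The same two, sandwich SE |
|---|---|---|---|---|
| 18/18/18/18 | 4.6% | 4.8% | 4.7% | 4.6–4.7% |
| 15/16/17/18 | 4.9% | 5.0% | 7.2% | 4.9% |
| 12/14/15/18 | 4.3% | 4.2% | 9.7% | 4.4% |

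In the last row the mean model-based standard error was 1.48, against an actual spread of 1.76. A smaller simulation (600 trials per setting, Monte Carlo SE about 1 point) gave 4.7% to 7.0% with the sandwich.

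**6. How likely the later fallbacks are.** For four visits, unstructured needs 4 × 5/2 = 10 covariance parameters and heterogeneous Toeplitz 4 + 3 = 7, with 400 to 480 participants. Both should normally converge.

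**The case against.** The strongest reply is that the SAP already has a safeguard. Heterogeneous Toeplitz comes first in the list, allows a separate variance at each visit, and does not inflate the error. Two successive convergence failures are needed, and the primary fit has ample data. That stands, and it is the main reason for the low priority.

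Several stronger readings are tempting, and the documents do not support them:
- *Failure of the unstructured fit alone inflates the error.* It does not. The next structure is at or below about 5%.
- *The error doubles.* That needs early SDs near two thirds of the Week 12 value (12 against 18). No SD for Weeks 2, 4 or 6 is given. Equal SDs give 5%, and falling SDs give less.
- *Kenward-Roger assumes equal variances.* The assumption belongs to the covariance structure. Kenward-Roger serves the unstructured and heterogeneous fits equally.
- *The Week 12 step-count model has many intervals and so is fragile.* By SAP Table 1 it has five post-baseline two-week intervals (Days 15 to 84), equally spaced, which is 15 unstructured parameters. SAP 5.3.3 also gives a two-sided t-test that does not use this covariance.

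It is also fair to say that the subgroup and KCCQ domain analyses carry no protected 5% error rate. Their confidence intervals should still have the stated coverage. Small cells, such as age 18–25 in SAP 2.4, are where the later fallbacks are more plausible. No convergence rate was computed for them.

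**Conclusion.** The point holds as a conditional weakness of low likelihood. The second and third fallbacks tie the Week 12 test to an equal-variance assumption that is not part of the hypothesis, and nothing in the SAP corrects for it. If they are reached, the actual two-sided error runs from about 4% to about 13%, and is 6% to 7% for a moderate rise in SD. These figures rest on the document's SD of 18 at Week 12 and on assumed earlier SDs and correlations.

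A reader might infer that the primary 5% level, or the gate to step count, is compromised as the plan stands. It is not. The unstructured analysis and the first fallback both keep the error at about 5% or below.

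**What to change.** Add to SAP 5.2.3:

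> If a structure other than unstructured is used, standard errors, confidence intervals and p-values will be based on the empirical (sandwich) estimator, with compatible (non-Kenward-Roger) degrees of freedom and a small-sample correction in small subgroups.

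State that the same rule applies to the subgroup, KCCQ domain and step-count MMRMs.

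The cost is one sentence and one SAS option (EMPIRICAL in PROC MIXED). The downside is that sandwich errors are slightly less precise and can be slightly liberal in very small cells, hence the small-sample correction. They also repair only the standard error. They do not remove any bias that a wrong covariance can cause in the estimate when dropout depends on earlier scores.

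Replacing the two common-variance structures with heterogeneous AR(1) or heterogeneous compound symmetry is optional once the sandwich is specified. For four visits each needs 5 parameters, against 4 for standard Toeplitz. They too impose a correlation pattern that ignores the unequal visit gaps, so they do not replace the robust standard error.
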